10.2.2 Adverse Event Overview

An overview of TEAEs by treatment groups in each period will be presented consisting of the number and percentage of subjects experiencing at least one event for each of the following TEAE categories:

- Any treatment-emergent AE
- Any treatment-emergent AE related to study drug according to the investigator
- Any severe treatment-emergent AE
- Any serious treatment-emergent AE
- Any treatment-emergent AE leading to discontinuation of study drug
- Any treatment-emergent AE under the Areas of Safety Interest, as defined in [Appendix B](#)

- Any treatment-emergent AE leading to death
- Any COVID-19 related TEAEs

All deaths will also be summarized:

- COVID-19 related deaths
- Deaths occurring \leq 140 days after last dose of study drug
- Deaths occurring $>$ 140 days after last dose of study drug.

10.2.3 Treatment-Emergent Adverse Events by SOC and/or PT

Treatment-emergent adverse events will be summarized by SOC and PT; by maximum relationship to study drug as assessed by the investigator (e.g., reasonable possibility or no reasonable possibility) and by SOC and PT; by maximum severity and by SOC and PT; and by SOC and PT listing associated subject number. When summarizing the number and percentages of subjects, subjects with multiple occurrences of the same adverse event will be counted once, and only the maximum severity level will be presented in the severity summaries, and the worst/highest relationship level in the relationship summaries.

In addition, treatment-emergent adverse events will be summarized by PT and sorted by decreasing frequency for the active group.

10.2.4 Treatment-Emergent Adverse Events per Patient-Years of Exposure

Exposure-adjusted TEAEs per 100 patient-years will be provided, where TEAEs per 100 patient-years of exposure are defined as the number of TEAEs divided by the total exposure in 100 patient-years.

Note that one event per preferred term per day per subject will be counted in the calculation of the number of TEAEs (i.e., a preferred term will not be counted twice on

the same day for the same subject). The exposure-adjusted TEAE rate per 100 patient-years is calculated as:

$$100 \times \frac{\text{Number of TEAEs}}{\text{Total Patient Years}}$$

where total patient years in each period are defined below.

Total patient years in Period A: Sum of study drug exposure in Period A, defined as the minimum of (the last dose date in Period A + 140 days, the end of study date + 1 day, and the first dose date in Period B if not missing [and the cutoff date during the Primary Analysis + 1 day]) minus the first dose date in Period A, normalized by 365.25 and rounded to one decimal place.

Total patient years in Period B: Sum of study drug exposure in Period B, defined as the minimum of (the last dose date in Period B + 140 days, and the end of study date + 1 day [and the cutoff date during the Primary Analysis + 1 day]) minus the first dose date in Period B, normalized by 365.25 and rounded to one decimal place.

Total patient years in the All-Risankizumab Treated Period: Sum of study drug of risankizumab exposure, defined as the minimum of (the last risankizumab dose date + 140 days, and the end of study date + 1 day [and the cutoff date during the Primary Analysis + 1 day]) minus the first risankizumab dose date, normalized by 365.25 and rounded to one decimal place.

10.2.5 SAEs (Including Deaths) and Adverse Events Leading to Study Drug Discontinuation

Treatment-emergent SAEs (including deaths) and AEs leading to study drug discontinuation will be summarized by SOC and PT and in listing format.

A listing of pre-treatment SAEs with onset dates prior to the first dose of study drug will be provided.

10.2.6 Area of Safety Interest

Detailed information about the search criteria for areas of safety interest (ASIs) are provided in [Appendix B](#).

The final list will be based on the most updated final version of risankizumab Product Safety Statistical Analysis Plan, which is consistent to the most updated risankizumab Risk Management Plan.

Tabular listings of selected area of safety interest will be provided.

10.3 Analysis of Laboratory Data

Data collected from central and local laboratories, including additional laboratory testing due to an SAE, will be used in all analyses, except for Baseline derivation where SAE-triggered laboratory assessments on or before the first dose of study drug will be excluded. The clinical laboratory tests defined in the protocol operations manual (e.g., hematology and clinical chemistry) will be summarized.

Mean change from Baseline to each applicable post-baseline visit will be summarized for selected laboratory variables. The following descriptive statistics will be presented by treatment groups: number of observations, Baseline mean, visit mean, mean change from Baseline and its standard error, and the 95% confidence interval of the mean change from Baseline.

In addition, laboratory parameters will be tabulated using shift tables from Baseline to minimum and maximum values in each period (Period A and Period B), categorized by the toxicity grade according to NCI CTCAE Version 4.03³ of the laboratory used for each sample. A similar shift table will also be provided to summarize shifts from Baseline to the final post-baseline value in each period.

Laboratory abnormalities meeting CTC criteria grade 3 and 4 at least once in each period will be summarized.

Laboratory abnormalities will be evaluated based on Potentially Clinically Important (PCI) criteria ([Appendix C](#)). For each laboratory PCI criterion, the number and percentage of subjects who have a laboratory value meeting the criteria at least once in each period will be summarized. Listings will be provided to summarize subject-level laboratory data for subjects meeting PCI criteria.

In addition, the frequencies and percentages of subjects with post baseline liver specific function test values in ALT/SGPT, AST/SGOT, alkaline phosphatase, and total bilirubin that meet the following criteria will be summarized by treatment groups:

- $ALT > 3.0 \times ULN$
- $ALT > 5.0 \times ULN$
- $ALT > 10.0 \times ULN$
- $ALT > 20.0 \times ULN$
- $AST > 3.0 \times ULN$
- $AST > 5.0 \times ULN$
- $AST > 10.0 \times ULN$
- $AST > 20.0 \times ULN$
- Alkaline phosphatase $> 1.5 \times ULN$
- Total bilirubin $> 1.5 \times ULN$
- Total bilirubin $> 2.0 \times ULN$
- ALT and/or AST $> 3.0 \times ULN$ and Total bilirubin $> 1.5 \times ULN$
- ALT and/or AST $> 3.0 \times ULN$ and Total bilirubin $> 2.0 \times ULN$
- ALT $> 3 \times ULN$ and Total bilirubin $> 1.5 \times ULN$
- ALT $> 3 \times ULN$ and Total bilirubin $> 2.0 \times ULN$

A listing of potentially clinically important (PCI) liver function laboratory values will include all subjects who met any of the following four criteria:

- ALT $> 3.0 \times ULN$, or
- AST $> 3.0 \times ULN$, or

- ALP > 1.5 × ULN, or
- Total bilirubin > 1.5 × ULN.

A listing of possible Hy's Law cases, defined as those who meet all of the following conditions will be provided.

- ALT of > 3.0 × ULN or AST of > 3.0 × ULN,
- Total bilirubin ≥ 2.0 × ULN

10.4 Analysis of Vital Signs

Vital sign measurements of systolic and diastolic blood pressure will be summarized.

Change from baseline to each applicable post-baseline visit will be summarized for each vital sign variable. The following descriptive statistics will be presented by treatment groups: number of observations, Baseline mean, visit mean, mean change from Baseline and its standard error, and the 95% confidence interval of the mean change from Baseline.

Vital sign variables will be evaluated based on potentially clinically important (PCI) criteria ([Appendix D](#)). For each vital sign PCI criterion, the number and percentage of subjects who have a vital sign value meeting the criteria at least once in each period will be summarized. Listings will be provided to summarize subject-level vital sign data for subjects meeting PCI criteria.

10.5 Safety Subgroup Analyses

No subgroup for safety analyses.

10.6 Other Safety Analyses

No other safety analyses.

11.0 Other Analyses

No other analyses.

12.0 Interim Analyses

12.1 Data Monitoring Committee

There is no data monitoring committee (DMC) planned in this study.

13.0 Overall Type-I Error Control

The Primary Analysis will be the only and final analysis for the primary and all ranked secondary efficacy endpoints.

Overall type-I error will be controlled by testing the primary efficacy endpoint, followed by the ranked secondary efficacy endpoints, in a hierarchical order as described in Section 9.3 and Section 9.4.

14.0 Version History

Table 4. SAP Version History Summary

Version	Date	Summary
1.0	07 April 2021	Original version
2.0	11 July 2022	Clarified the time point of conducting Primary Analysis in Section 2.2. Clarified in Section 9.5 that categorical endpoints in Period B will be summarized by NRI-C, and continuous endpoints in Period B will be summarized by OC. Updated summary criteria in Section 10.3 based on PSSAP 5.0. Corrected a format issue in Table C-2.
3.0	16 May 2023	Due to MedDRA version update, CMQ codes in Appendix B. Safety Topics of Interest were updated accordingly.

Appendix A. Protocol Deviations

The number and percentage of subjects who reported at least one of the following protocol deviation categories will be provided.

- Subject entered into the study even though s/he did not satisfy entry criteria.
- Subject developed withdrawal criteria during the study and was not withdrawn.
- Subject received wrong treatment or incorrect dose of study.
- Subject took prohibited concomitant medication.

Appendix B. Safety Topics of Interest

Area of safety interest (ASI) will be identified using the following search criteria:

Area of Safety Interest	Search Criteria	
MACE	Adjudicated terms will be identified as described in PSSAP Table 4 using CECAT and CETERM from the CE SDTM dataset.	
Extended MACE	Adjudicated terms will be identified as described in PSSAP Table 3 (for MACE +) using CECAT and CETERM from the CE SDTM dataset.	
Serious Infections	Serious AEs in the Infections and Infestations SOC	
Active Tuberculosis	Active Tuberculosis CMQ (code 1000002)	
Opportunistic Infections excluding tuberculosis and herpes zoster	Opportunistic infection excluding tuberculosis and herpes zoster CMQ (code 1000105)	
Injection Site Reactions	Narrow	Injection site reaction CMQ (code 1000091)
Malignant Tumours	Narrow	Malignant tumours (SMQ 20000194)
Non-melanoma Skin Cancer (NMSC)	Broad	Skin malignant tumours (SMQ 20000204) excluding terms identified by the Melanoma CMQ (code 1000100)
Malignant Tumours excluding NMSC	'Malignant Tumours excluding NMSC' is identified by the 'Malignant Tumours' search excluding terms identified by the 'Non-melanoma skin cancer (NMSC)' search.	
Hypersensitivity	Narrow	Hypersensitivity (SMQ 20000214)
Serious hypersensitivity reactions	Narrow	Serious AEs in the Hypersensitivity (SMQ 20000214)
Adjudicated Anaphylactic Reaction*	Adjudicated terms will be identified using SDTM data (e.g., CE and PR domains).	
Hepatic Events	Broad	Hepatic failure, fibrosis and cirrhosis and other liver damage-related conditions (SMQ 20000013)
	Broad	Hepatitis, non-infectious (SMQ 20000010)
	Broad	Cholestasis and jaundice of hepatic origin (SMQ 20000009)
	Broad	Liver related investigations, signs and symptoms (SMQ 20000008)
	Narrow	Liver-related coagulation and bleeding disturbances (SMQ 20000015)

* Events will be identified for adjudication by Anaphylactic Reaction SMQ Broad search as specified in the RISA AAC Charter.

Appendix C. Potentially Clinically Important Criteria for Safety Endpoints

The criteria for Potentially Clinically Important (PCI) laboratory findings are described in Table C-1 and Table C-2.

Table C-1. Criteria for Potentially Clinically Important Hematology Values

Hematology Variables	Units	Definition of Potentially Clinically Important: NCI CTCAE (Version 4) Grade 3 or Greater
		Very Low
Hemoglobin	g/dL	< 8.0
Platelets count	$10^9/L$	< 50.0
WBC count	$10^9/L$	< 2.0
Neutrophils	$10^9/L$	< 1.0
Lymphocytes	$10^9/L$	< 0.5

Note: A post-baseline grade must be more extreme than the baseline grade to be considered a potentially clinically important finding.

Table C-2. Criteria for Potentially Clinically Important Chemistry Values

Chemistry Variables	Units	Definition of Potentially Clinically Important: NCI CTCAE (Version 4) Grade 3 or Greater	
		Very Low	Very High
Total Bilirubin	mcmol/L		$> 3.0 \times \text{ULN}$
ALP	U/L		$> 5.0 \times \text{ULN}$
SGOT/AST	U/L		$> 5.0 \times \text{ULN}$
SGPT/ALT	U/L		$> 5.0 \times \text{ULN}$
Albumin	g/L	< 20	
Glucose	mmol/L	< 2.2	> 13.9
Triglycerides	mmol/L		> 5.7
Creatinine	mcmol/L		$> 3.0 \times \text{ULN}$ or $> 3.0 \times \text{baseline}$
Sodium	mmol/L	< 130	> 155
Potassium	mmol/L	< 3.0	> 6.0
Calcium	mmol/L	< 1.75	> 3.1
CPK	U/L		$> 5.0 \times \text{ULN}$
Total Cholesterol	mmol/L		> 10.34
GGT			$> 5.0 \times \text{ULN}$

Note: A post-baseline grade must be more extreme than the baseline grade to be considered a potentially clinically important finding.

Appendix D. Criteria for Potentially Clinically Important Vital Sign Values

Vital Signs Variables	Criterion	Definition of Potentially Clinically Important
Systolic Blood Pressure (mmHg)	Low	Value \leq 90 mmHg and decrease \geq 20 mmHg from Baseline
	High	Value \geq 160 mmHg and increase \geq 20 mmHg from Baseline
Diastolic Blood Pressure (mmHg)	Low	Value \leq 50 mmHg and decrease \geq 10 mmHg from Baseline
	High	Value \geq 100 mmHg and increase \geq 10 mmHg from Baseline

Appendix E. Non-Responder Imputation Incorporating Multiple Imputation to Handle Missing Data Due to COVID-19 Pandemic for Dichotomized Outcome Variables

1.0 Overview

1.1 Background and Justification for Missing at Random (MAR) Assumption

The COVID-19 pandemic is interfering with the conduct of many ongoing trials, with potential impacts on treatment duration and the collection, analysis and the interpretation of clinical trial data. Some protocol-specified visits in the clinical trials may be impacted due to COVID-19 infection or logistical restrictions during the pandemic. For example, some scheduled visits may be missed due to self-quarantine or local government restrictions on travel; some visits may also be delayed or canceled due to healthcare resource constraints during the pandemic. Impacted visits due to COVID-19 will be recorded in the database. The probability of having missed visits and missing data due to COVID-19 infection or logistical restrictions related to the COVID-19 pandemic can be reasonably assumed to be unrelated to the unobserved values. Therefore, for the purpose of statistical analysis, it is reasonable to assume that these missing data are missing at random (MAR) and the statistical models that require MAR assumption are appropriate. In some cases, sensitivity analyses may be performed to assess the impact of missing data and the robustness of the conclusion.

1.2 FDA Guidance

FDA provided two guidance documents^{1,2} in March 2020 and June 2020 on the efficacy collection and possible changes in the statistical analysis plan:

- "With respect to efficacy assessments, FDA recommends consultation with the appropriate review division regarding protocol modifications for the collection of efficacy endpoints, such as use of virtual assessments, delays in assessments, and alternative collection of research-specific specimens, if feasible. For individual instances where efficacy endpoints are not collected, the reasons for failing to obtain the efficacy assessment should be documented (e.g.,

identifying the specific limitation imposed by COVID-19 leading to the inability to perform the protocol-specified assessment)."

- "If changes in the protocol will lead to amending data management and/or statistical analysis plans, the sponsor should consider doing so in consultation with the applicable FDA review division. Prior to locking the database, sponsors should address in the statistical analysis plan how protocol deviations related to COVID-19 will be handled for the prespecified analyses."

1.3 EMA Guidance

EMA provided guidance³ in March 2020:

- "At this point in time it is not possible to give general applicable advice on how the different aspects related to the pandemic should be handled, as implications on clinical trials are expected to be manifold. Impact on the data collection, analysis and interpretation of results for each trial will need a thorough case-by-case assessment."
- "As a general principle, there are strong scientific reasons to conduct trials as planned and implement changes only when there is a convincing scientific reason that it improves interpretability of results."

1.4 Missing Data Handling for Missing Due to COVID-19 for Dichotomized Variables

In this document, a missing data handling method is proposed to handle missing data due to COVID-19 infection or logistical restrictions related to the COVID-19 pandemic under the general MAR framework. In particular, we explain using multiple imputation (MI) to handle missing data due to COVID-19 in dichotomized variables in conjunction with non-responder imputation (NRI) for missing data due to other reasons.

2.0 Non-responder Imputation Incorporating Multiple Imputation (NRI)

2.1 Overall Description of the Method

For a dichotomized outcome variable with missing data, the NRI will categorize any subject who does not have evaluation during a pre-specified visit window as a non-responder for the visit, with two exceptions:

- If the subject is a responder both before and after the pre-specified visit window in the particular Study Period, the subject will be categorized as a responder for the visit.
- If the reason for missing (e.g., missed visits, incomplete visit, out-of-schedule visits, or discontinuations of study drug) is due to COVID-19, the information will be captured in the database and the subject's response status will be imputed using multiple imputation.

Subjects whose change/percent change from Baseline cannot be calculated because of a missing Baseline will be considered as a non-responder at all post-baseline visits, unless the post-baseline value is zero.

Non-responder imputation incorporating multiple imputation (NRI) for missing due to COVID-19 will be implemented as follows.

2.2 Multiple Imputation (MI) and MAR Assumption

When a dichotomized variable is derived from a continuous scale, for example, PPASI 75 (at least a 75% reduction in PPASI relative to Baseline), the multiple imputation will be applied to the original scale, PPASI (ranges from 0 – 72) assuming multivariate normal distribution. Then the dichotomized variable will be derived from the imputed value.

The MI procedure assumes that the data are missing at random (MAR). That is, for an outcome variable Y, the probability that an observation is missing depends only on the

observed values of other variables, not on the unobserved values of the outcome variable Y. Statistical inference from the MI procedure is valid under the MAR assumption.

2.3 Imputation Algorithm

It is reasonable to assume the missing values of the longitudinal data for an outcome variable (e.g., PPASI, the original scale of PPASI 75, at each post-baseline visit) follows a monotone missing pattern. In practice, the missing data of the outcome variable might have an arbitrary (non-monotone) missing data pattern. An extra step may be added accordingly, to augment data into a monotone missing pattern.

For the outcome variable (e.g., PPASI at each visit), K 'complete' datasets can be generated in two steps: augmentation step and imputation step. K, the number of repetitions, is determined below.

Augmentation Step

For datasets with non-monotone missing data pattern, the augmentation step will first impute enough values to augment the data into a monotonic missing pattern:

Markov Chain Monte Carlo (MCMC) will be applied to augment the data using PROC MI with the MCMC IMPUTE=monotone statement, assuming a multivariate normal distribution. The augmented data will be used in the subsequent imputation step to generate 'complete' datasets. Covariates included in the model are treatment group, Baseline BSA, Baseline ppIGA category, Baseline (if other than Baseline ppIGA), and all post-baseline visits of the outcome variable up to the end of the Study Period. Of note, categorical variables are included using the form of dummy variables.

Repeat the imputation process K=30 times using the procedure described above to form K=30 monotone missing datasets, where K is determined as described in "Repetition of Imputations (K)."

Imputation Step

For missing data with monotone missing patterns, the choice of multiple imputation using a parametric regression model that assumes multivariate normality is appropriate.

The imputation step is described below:

- The imputation model for the missing data is a regression model, which controls for treatment group, Baseline BSA, Baseline ppIGA category, Baseline (if other than Baseline ppIGA), and all post-baseline visits of the outcome variable up to the end of the Study Period. The covariates included in the model and the order of these variables are consistent with the augmentation step.
- For each monotone missing dataset, using SAS PROC MI with MONOTONE REG model statement, the outcome variable at each post-baseline visit with missing values will be imputed sequentially with covariates constructed from their corresponding sets of preceding variables.

A 'complete' dataset with imputed values for the missing data is generated after the augmentation and imputation steps are completed.

Repetition of Imputations (K)

Repetition of imputations, K , must be determined in advance. When estimating the overall variance of multiple imputation, the additional sampling variance is the between-imputation variance divided by K . This value represents the sampling error associated with the overall or average coefficient estimates. It is used as a correction factor for using a specific number of imputations. The more imputations (K) are conducted, the more precise the parameter estimates will be. For example, with a 1% power falloff tolerance in multiple imputation, as compared to an infinite number of imputations, multiple imputation requires 20 repetitions of imputation for 30% missing information and 40 repetitions for 50% missing information (Graham, Olchowski, and Gilreath 2007⁴). In the usual clinical settings expecting less than 30% missing information, $K=30$ repetitions

are deemed sufficient. When missingness exceeds 30%, depending on the power falloff tolerance level, number of repetitions may need to be increased. Recent research⁴ suggested that the number of repetitions (K) should be at least equal to the percentage of missing (White et al., 2011⁶).

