2.4 Sample Size Determination

The ppIGA is an endpoint that has been used in another clinical trial in the palmoplantar psoriasis population and which is based on the modified Investigator's Global Assessment version of 2011.^{1,2} Given the lack of historical ppIGA data from risankizumab trials, the assumption of response rates in the current study are based on the relevant endpoints of PPASI 75 and PPASI 90 from risankizumab PsO Studies M15-992, M15-995, and M16-008, among subjects who had Baseline PPASI of at least 8. Among these subjects, approximately 80% and 75% of subjects from the risankizumab (RZB) group achieved PPASI 75 and PPASI 90, respectively; compared to 50% and 40% in the placebo (PBO) group.

Assuming that 75% of subjects from the RZB group and 45% of subjects from the PBO group would achieve the primary endpoint of ppIGA of 0 or 1 with at least a 2-point reduction from Baseline at Week 16, the sample size of 168 subjects (84 subjects per group) will provide more than 90% power to detect the treatment difference between RZB and PBO, under a 2-sided significance level of 0.05.

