2.4 Derivation of Response Status and Non-Responder Imputation

For each 'complete' dataset, the imputed post-baseline values will be rounded to the same precision as the observed data. Response status (e.g., PPASI 75 at each visit) will be determined accordingly.

The imputed response status for missing due to reasons other than COVID-19 will be overridden by non-responder imputation (Section 2.1) to ensure that multiple imputation is only applied to missing due to COVID-19:

- Using NRI approach, all missing due to reasons other than COVID-19 will be categorized as non-responders. In addition, subjects whose change/percent change from Baseline cannot be calculated because of a missing Baseline will be considered as a non-responder at all post-baseline visits, unless the post-baseline value is zero.
- The only exception is that a subject will be categorized as a responder for the visit if the subject is a responder both before and after an SAP-specified visit window in the particular Study Period.

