3.0 Sample SAS Code

```

/*****/
/*IMPUTATION ALGORITHM*/
/*****/
/*NOTE: THIS APPROACH REQUIRES NO MISSING IN CATEGORICAL COVARIATES AND
REQUIRES AT LEAST ONE OBSERVATION IN BASELIBE OR ONE OF THE POST-
BASELINE VISIT*/

/*PRE-AUGMENTATION - CREATE DUMMY FOR CATEGORICAL VARIABLES*/
/*****/
DATA PPASI_2; SET PPASI;
  /*THE MCMC STATEMENT BELOW ASSUMES MULTI-VARIATE NORMAL*/
  IF TRT01PN=1 THEN TRT1=1; ELSE TRT1=0;
  /*BASELINE BSA and BASELINE PPIGA CATEGORY*/
  IF BSAGR1N = 1 THEN REG1 = 1 ;ELSE REG1 = 0;
  IF PPIGAGR1N = 1 THEN REG2 = 1 ;ELSE REG2 = 0;

RUN;

/*AUGMENTATION STEP -- TO HAVE 30 MONOTONE MISSING DATASETS*/
PROC MI DATA= PPASI_2 OUT= PPASI_MONO NIMPUTE=30 SEED= 21423 /*RANDOM
SEED PRE-DEFINED*/
  ROUND=. . . 0.1 0.1 0.1 /*VALUE ROUND TO 1ST DECIMAL*/
  MIN=. . . 0 0 0 /*MINIMUM VALUE OF PPASI IS 0*/
  MAX=. . . 72 72 72 /*MAXIMUM VALUE OF PPASI IS 72*/
MCMC IMPUTE=MONOTONE ;
/*NOTE: CATEGORICAL VARIABLES SUCH AS TRT1 TRT2 ARE DUMMY, CREATED
ABOVE*/
/*NOTE: ALL OTHER NON-DUMMIED COVARIATES MUST BE CONTINUOUS*/
/*SUPPOSE STRATAN (NUMERIC VARIABLE FOR STRATA) HAS ONLY 2 LEVELS, NO
NEED TO CREATE DUMMY*/
VAR TRT1 BSABL REG2 BASE WK4 WK16;
/*CAUTION TO USE THE "BY" STATEMENT IN MCMC: */
/*MVN MODEL IS FITTED WITHIN EACH 'BY' GROUP, INSTEAD OF ACROSS ALL
GROUPS*/
RUN;

/*IMPUTATION STEP - DETERMINE IMPUTATION DISTRIBUTION AND RANDOMLY
IMPUTE MISSING VALUE TO GENERATE 'COMPLETE' DATASETS*/
/*****/

```

```

PROC MI DATA= PPASI_MONO OUT= PPASI_FULL NIMPUTE=1 SEED= 21931 /*RANDOM
SEED PRE-DEFINED*/
  ROUND= . . . 0.1 0.1 0.1 /*VALUE ROUND TO 1ST DECIMAL*/
  MIN=. . . 0 0 0 /*MINIMUM VALUE OF PPASI IS 0*/
  MAX=. . . 72 72 72 /*MAXIMUM VALUE OF PPASI IS 72*/
  MINMAXITER=1000;
  /*CLASS CATEGORICAL VARIABLES TRT1 AND REG2*/
  CLASS TRT1 REG2;
  VAR TRT1 BSABL REG2 BASE WK4 WK16;
  MONOTONE REG (WK4 WK16); /* IMPUTED SEQUENTIALLY, FROM WK 4 TO 16,
WITH COVARIATES CONSTRUCTED FROM THE CORRESPONDING PRECEDING VARIABLES*/
  BY _IMPUTATION_ ; /*FOR EACH OF THE 30 MONOTONE
MISSING DATASETS, IMPUTE A 'COMPLETE' DATASET*/
RUN;

/*DETERMINE DICHOTOMOUS RESPONSE STATUS, PPASI 75 AT WEEK 16*/
DATA ALL; SET PPASI_FULL;
  IF 0<=WK16<=0.25*BASE THEN PPASI75_16=1;
  ELSE PPASI75_16=0;
RUN;

/*****
*/
/*          DATA HANDLING STEPS TO MERGE COVID-19 STATUS OMITTED
*/
/*          PLACE TO ADD DATA HANDLING AND MERGING STEPS
*/
/*****
*/

/*FOR MI, SKIP THE FOLLOWING CODE, PROCEED TO THE CODE AFTER ANALYSIS

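### Normal-regression imputation of raw PPASI understates PPASI 90 among COVID-19-missing subjects at the SAP's historical rates, and nearly eliminates PPASI 100 if out-of-range draws are redrawn

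*SAP*

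**What the plan says.** SAP Appendix E 2.2 applies multiple imputation to the original PPASI scale (0 to 72), "assuming multivariate normal distribution. Then the dichotomized variable will be derived from the imputed value". Section 2.3 adds that, for monotone missing patterns, "the choice of multiple imputation using a parametric regression model that assumes multivariate normality is appropriate". The covariates are treatment, Baseline BSA, Baseline ppIGA category, Baseline score and the post-baseline visits.

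The sample code in Appendix E 3.0 uses "MONOTONE REG (WK4 WK16", rounds to 0.1, sets an upper bound of 72 and a lower bound ("MIN=. . . 0 0 0 /*MINIMUM VALUE OF PPASI IS 0"), and gives "MINMAXITER=1000" as an iteration limit. Treatment enters as a covariate. The code comments that under a BY statement the "MVN MODEL IS FITTED WITHIN EACH 'BY' GROUP", and there is no BY on arm, so one model serves both arms.

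Section 2.4 of the appendix overrides every other imputed status with non-response, "to ensure that multiple imputation is only applied to missing due to COVID-19".

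SAP 2.4 (sample size) reports, for earlier-trial subjects with Baseline PPASI of at least 8, that "approximately 80% and 75% of subjects from the risankizumab (RZB) group achieved PPASI 75 and PPASI 90, respectively; compared to 50% and 40" per cent on placebo. PPASI 90 and PPASI 100 are ranked secondary endpoints 2 and 4 (SAP 3.2). SAP 9.4.3 marks sensitivity analyses of the ranked secondary endpoints as not applicable.

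**The concern.** PPASI 90 means a Week 16 score at or below 10% of Baseline. If 75% of one arm and 40% of the other are there, the distribution is a heap at and near 0 with a long right tail. A normal regression predicts the mean, which the tail pulls up, and spreads draws symmetrically around it. Too few draws then fall at or below 10% of Baseline. PPASI 100 needs a value that rounds to exactly 0.0, which a continuous draw kept at or above 0 seldom gives.

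The MAR argument in Appendix E does not cover this. Valid inference also needs an imputation model that fits, and the shortfall appears even when values are missing completely at random.

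At stake is the purpose of the rule. COVID-19-missing subjects go to multiple imputation so that they are not counted as failures. With redraws, PPASI 100 comes close to counting them as failures anyway, without saying so.

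**Working it through.** **Plan's own figure.** Two-proportion power = Φ[(p1 − p2 − 1.96·SE0)/SE1], with SE0 pooled and SE1 unpooled. For 84 per arm and 75% v 45%: (0.30 − 1.96 × 0.0756)/0.0720 = 2.11, giving 98.3%. This agrees with the stated figure of more than 90%.

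**Inputs.** From the documents: PPASI 75/90 of 80/75% and 50/40%, Baseline PPASI at least 8, bounds 0-72, rounding 0.1, 84 per arm, K = 30. Not in the documents, and so assumed and varied: Baseline distribution, spread of non-responders, Week 4 correlation, PPASI 100 rates and the COVID-19-missing share.

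**Hand check, PPASI 90.** Assume Baseline 12 in the risankizumab arm, with PPASI 90 responders averaging 3% of Baseline, the next 5% of subjects 17.5%, and the remaining 20% of subjects 60%.
- Mean = 12 × (0.75 × 0.03 + 0.05 × 0.175 + 0.20 × 0.60) = 1.8. The cutoff is 1.2.
- The mean lies above the cutoff, so fewer than half of the normal draws can be responders, against a true 75%.
- Residual SD 3 (assumed), draws below 0 set to 0: Φ((1.2 − 1.8)/3) = 42%.
- Same, redrawn: (Φ(−0.2) − Φ(−0.6))/(1 − Φ(−0.6)) = (0.421 − 0.274)/0.726 = 20%.

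**Hand check, PPASI 100 with redraws.** The draw must fall between 0 and 0.05: P = [Φ((0.05 − μ)/σ) − Φ(−μ/σ)]/[1 − Φ(−μ/σ)].

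| Predicted mean | SD 2 | SD 5 |
|---|---|---|
| 0 | 2.0% | 0.8% |
| −1 SD | 3.8% | 1.5% |
| −2 SD | 5.8% | 2.35% |

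These low values hardly depend on the assumed inputs.

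**Simulated rates among imputed subjects**, true PPASI 90 about 75% risankizumab and 40% placebo:

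| Draws outside 0-72 | PPASI 90 risankizumab | PPASI 90 placebo | PPASI 100 risankizumab |
|---|---|---|---|
| Redrawn | 11-45% | 6-26% | 0.2-3.4% |
| Set to the bound | 40-53% | 22-25% (narrower set of runs) | 25-40% |

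The assumed true PPASI 100 was 35-50% v 10-20%. Making missingness depend on a poor Week 4 score gave 10-31% for risankizumab PPASI 90 with redraws (true 60-74%). In stress cases where Week 4 almost determines Week 16 (R² 0.90-0.98), redraws gave 47-72% for PPASI 90 and at most 8.6% for PPASI 100. The gap narrows but does not close.

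**Trial level.** Mean loss in the difference = missing share × (true difference − imputed difference) among missing subjects. From one set of runs with redraws:

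| Assumed missing | PPASI 90 difference, full → imputed | Loss (points) | PPASI 100 difference, full → imputed | Loss (points) |
|---|---|---|---|---|
| 2% | 34.27 → 33.75 | 0.5 | 20.43 → 20.07 | 0.4 |
| 5% | 34.61 → 33.30 | 1.3 | 20.42 → 19.38 | 1.0 |
| 10% | 34.88 → 32.06 | 2.8 | 20.15 → 18.24 | 1.9 |

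With draws set to the bound, the losses at 10% are 1.5 points for PPASI 90 (34.88 → 33.40) and 0.1 for PPASI 100 (20.15 → 20.04). Across the assumptions, the mean loss with redraws is about 0.4-0.6 points at 2% and 1.7-2.9 at 10%.

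**Ceiling.** The imputed difference is not negative, so on average the loss cannot exceed that of plain non-responder imputation, which is the missing share times the true difference. For PPASI 90 this is 0.02 × 35 = 0.7, 0.05 × 35 = 1.75 and 0.10 × 35 = 3.5 points. The per-trial SD of the loss at 2% is about 1.0 point, so 110 simulated trials carry a standard error near 0.1. Individual simulated results above the ceiling are noise.

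**Tests.** At that ceiling with 10% missing, the same power formula gives:
- PPASI 90: 75% v 40% becomes 67.5% v 36%; power goes from 99.8% to 98.7%.
- PPASI 100 at an assumed 35% v 10%: becomes 31.5% v 9%; power goes from 97.8% to 95.9%.

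**The case against.** The strongest reply is that this hardly matters. At 2% missing, fewer than two subjects per arm are imputed. At 10%, the PPASI 90 loss is under 3 points against a standard error of about 7.1 points for the difference. The bias is conservative, and the worst PPASI 100 outcome is roughly the non-responder rule that the SAP already accepts for other missing data. All of this stands, and it limits the point to the accuracy of reported rates.

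Second, the historical rates may be too high here. Those trials required BSA of at least 10%, while this one admits 1%. At assumed PPASI 75/90/100 rates of 45/30/15% v 15/8/3%, the losses at 10% missing were 1.7-1.8 points (PPASI 90) and 1.1-1.2 (PPASI 100), against 2.5-2.6 and about 2.8 at the historical rates in the same runs. The direction holds; the size shrinks.

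Third, a reader might infer that PPASI 100 responders are bound to vanish. The documents do not support that. Bounds and iteration limit stand only in sample code written for PPASI 75, and the text gives no rule for out-of-range draws. Setting them to 0 removes most of the PPASI 100 shortfall. So might an unbounded draw if a negative value counted under the definition in Protocol Appendix A (improvement of 100% or more). PPASI 90 stays low with redraws and with draws set to 0. It is also low, at 9-11% on risankizumab, with no bounds and the code's requirement that the value be at least 0.

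Fourth, the sentence in Appendix E 2.3 ties the method to a monotone pattern and does not assert that PPASI is normal. That is fair, but 2.2 makes the normality assumption and neither section checks it.

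A plain non-responder sensitivity analysis would be simpler, but with redraws its PPASI 100 difference lies within 0.2 points of the planned result in every main scenario. The agreement would look like robustness.

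**Conclusion.** The concern holds in a limited form. If Week 16 PPASI is heaped near 0, as the SAP's historical rates imply, the planned imputation gives too low a PPASI 90 rate whether out-of-range draws are redrawn or set to 0. It gives almost no PPASI 100 responders if they are redrawn. At the historical rates with redraws, each treatment difference loses about 0.4-0.6 points at 2% missing and 1.7-2.9 at 10%. The missing shares, the PPASI 100 rates, the Baseline distribution and the Week 4 correlation are assumptions. With no COVID-19-missing Week 16 PPASI, nothing changes.

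A reader might go on to infer inflated type I error, a likely failed test or a biased primary endpoint. None is supported: the bias is toward the null, power stays high even at the ceiling, and ppIGA imputation was not assessed. No claim is made for PPASI 75, where the error changed sign across settings.

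**What to change.** For the PPASI endpoints only:
- In Appendix E 2.3 and 3.0, replace MONOTONE REG on raw PPASI with predictive mean matching (REGPMM, for example 5 donors) on percent change from Baseline, run within treatment arm. Covariates: Baseline BSA, Baseline ppIGA category, Baseline PPASI and Week 4 on the same percent scale. The treatment term drops out.
- Derive PPASI 75/90/100 from the one matched value, so that they stay nested.
- Rescale bounds and rounding in the MCMC augmentation step. The lower bound is −100%. The upper bound is 100 × (72 − b)/b, where b is the smallest Baseline PPASI actually randomized. At b = 8 this is +800%, and it is higher if anyone entered below 8.
- Amend the original-scale wording in 2.2 and the statement of appropriateness in 2.3.

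In 414 simulated scenarios this matching kept the difference within 0.5 points of full data for PPASI 90 and 0.7 for PPASI 100; in a separate set of runs both stayed within about 0.2. As a check on the cause, a logistic model for PPASI 90 status returned 73-75% among imputed risankizumab subjects against a true 74-76%.

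Cost: SAP wording and modest programming, with no new data. The donor pool is about 76-80 per arm (84 × 0.90 and 84 × 0.95). Missing Week 4 scores and the augmentation step were not tested. ppIGA and sPGA imputation is outside this point because it was not assessed.
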